APPENDIX 2. SAMPLE SAS CODE FOR RCM ANALYSIS

SAS code for this model, using the primary endpoint ppFVC as example, is provided below.

```

/*Random Coefficient Model (RCM) to estimate the change at year 1, 2, 3 and
4*/
/*avisityr is the actual number of years from Day 1, avisityr=4 will be
the change from baseline at year 4 */
/* fvc0= baseline ppFVC, should be used for change in FVC */
/* &meanfvc0= the mean of the baseline ppFVC           */

proc mixed data = fvc_obs;
  class subjid;
  model chgfvc = avisityr fvc0/solution cl covb outp=pred_fvc cl;
  random intercept avisityr /subject=subjid type=CS;
  ESTIMATE 'Change from Baseline at Year 1' intercept 1 avisityr 1 fvc0
  &meanfvc0 / CL;
  ESTIMATE 'Change from Baseline at Year 2' intercept 1 avisityr 2 fvc0
  &meanfvc0 / CL;
  ESTIMATE 'Change from Baseline at Year 3' intercept 1 avisityr 3 fvc0
  &meanfvc0 / CL;
  ESTIMATE 'Change from Baseline at Year 4' intercept 1 avisityr 4 fvc0
  &meanfvc0 / CL;
  ods output SolutionF=mxparms CovB=mxcovb Estimates=chgfrbl;
run;

```

Sample SAS code for comparison 079 OLE data (trt = 1) with CINRG (trt = 0).

```

PROC MIXED DATA = final;
  CLASS trt SUBJID ;
  MODEL chg = trt|avisityr base/ SOLUTION DDFM=KR;
  RANDOM intercept avisityr / SUBJECT =SUBJID TYPE=UN GROUP= trt;

  LSMEANS trt/ at avisityr = 1 PDIFF CL;
  LSMEANS trt/ at avisityr = 2 PDIFF CL;
  LSMEANS trt/ at avisityr = 3 PDIFF CL;
  LSMEANS trt/ at avisityr = 4 PDIFF CL;

  ods output LSMeans=LSMeans_chg diffss=diffs_chg;
RUN;

```

Statistical Analysis Plan

Addendum

TITLE PAGE

PROTOCOL TITLE: A Trial of FG-3019, a Monoclonal Antibody to Connective Tissue Growth Factor, in Non-Ambulatory Subjects with Duchenne Muscular Dystrophy (DMD)

PROTOCOL NUMBER: Protocol FGCL-3019-079

STUDY SPONSOR: FibroGen, Inc.
[name]
[name]

STUDY DRUG: Pamrevlumab

INDICATION: Duchenne Muscular Dystrophy (DMD)

SAP VERSION Addendum v1.1

RELEASE DATE August 08, 2023

[figure not shown]
CONFIDENTIALITY STATEMENT

The information contained in this document is confidential and proprietary to FibroGen, Inc. No part of this document or any of the information contained herein may be transmitted, disclosed, shared, reproduced, published or utilized by any persons without prior written authorization by FibroGen, Inc.

SIGNATURES AND APPROVALS**Approvals**

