## 1. PROTOCOL SYNOPSIS

Study Title:	Trial of Pamrevlumab (FG-3019), a Monoclonal Antibody to Connective Tissue Growth Factor, in Non-Ambulatory Subjects with Duchenne Muscular Dystrophy
Protocol Number:	FGCL-3019-079, Amendment 8.0
Investigational Product:	Pamrevlumab (FG-3019) (Recombinant fully human IgG1 kappa monoclonal antibody to connective tissue growth factor)
Study Phase:	Phase 2
Target Population:	Non-ambulatory subjects with Duchenne muscular dystrophy (DMD)
Number of Subjects Planned:	Approximately 22 subjects will be enrolled; interim analysis may increase sample size to approximately 32
Study Centers Planned:	Approximately 10 centers

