5. GENERAL STATISTICAL CONSIDERATIONS

5.1. Statistical Methodology

Continuous variables will be presented by descriptive statistics: n, mean, standard deviation, median, Q1-Q3, minimum, and maximum. Categorical variables will be tabulated by frequency count and percentage.

Lab results obtained from the central laboratory, rather than local laboratories, will be used for all efficacy and safety analyses. Some lab data are collected using local labs (in lieu of the ICON central lab) due to central lab kit shortages caused by the COVID-19 pandemic. In these cases, local lab values and reference ranges collected from CRFs will be integrated with central lab data when appropriate and feasible. Local lab values will be flagged in data sets and data listings to be differentiated from central lab values. Sensitivity analyses may be performed for key analyses of lab parameters without local lab values (e.g., set to missing).

Unless otherwise stated, all statistical tests will be two-sided hypothesis tests performed at the 5% level of significance for main effects and all confidence intervals will be two-sided 95% confidence intervals.

Unless otherwise specified, there will be no adjustments for multiple comparisons.

All data collected will be presented by data listings for review and substantiation of summary tables.

Safety and efficacy data will be summarized and presented by treatment group (pamrevlumab or source of external data, as applicable), and analysis visit in summary tables as appropriate.

All analyses will be performed using SAS® Version 9.4 or higher.

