9.2.2. Annual Change from Baseline to Week 208 in Efficacy Endpoints with RCM

The following endpoints will be analyzed with the same RCM analysis method.

1. Annual mean change from baseline in the Percent Predicted FVC (ppFVC)
2. Annual mean change from baseline in the total score of Performance of Upper Limb (PUL)
3. Annual mean change from baseline the Grip strength of the hands extremities assessed by Hand Held Myometry (HHM)
4. Annual mean change from baseline in cardiac fibrosis score assessed by Late Gadolinium Enhancement (LGE)
5. Annual mean change from baseline in Left Ventricular Ejection Fraction percentage (LVEF %) assessed by MRI
6. Annual mean change from baseline in Myocardial Circumferential Strain [Mean Peak Circumferential strain (MPCS) and Global Circumferential Strain (GCS) percentage] assessed by cardiac MRI

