9.2.2.1. Analysis Method

Annual mean change from baseline in the above efficacy endpoints each will be analyzed using Random Coefficient Model (RCM) analysis, and the estimated annual change from baseline values at year 1 through year 4 in the OLE period will be presented.

The model will include continuous variable avisityr (calculated as the elapsed days of assessment date from baseline date in the unit of year) and baseline endpoint as fixed effects, while the intercept and avisityr are included as random effects.

The unstructured covariance structure for the within-patient errors in the model will be applied first. The by-treatment-group option is included to the covariance pattern to improve the model efficiency.

If the algorithm for unstructured covariance pattern does not converge, the following covariance structures will be tested in sequence until the model converges: heterogeneous Toeplitz, homogeneous Toeplitz, first-order autoregressive, compound symmetry, and variance component. The sandwich estimator will be used if there is convergence issue. If the model does not converge for all covariance structures listed above, some least significant factors or interaction terms ($p>0.05$)

can be excluded from the model to achieve convergence. The revised model with fewer factors or interaction terms will be tested using the same sequence as specified above.

When the random effects model does not converge or do not have a positive definite Hessian, the fixed effects instead of random effects for the intercept and slope will be performed instead.

The LSMean (SE) and 95% CI for annual change (slope) as well as estimated changes from baseline at year-1, year 2, year 3 and year 4 (regarding week 52, week 104, week 156 and week 208) will be presented.

9.2.2.2. Handling of Intercurrent Events:

Treatment discontinuation (such as: due to AEs, Lost to Follow-Up, Withdrawal by subject, Physician Decision, Protocol Deviations, etc.): treatment policy: the occurrence of the intercurrent event is irrelevant. All observed values will be used regardless of whether or not the inter-current event occurs.

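### The single-arm random coefficient model names no degrees-of-freedom method, so its year 1–4 confidence intervals come out slightly too narrow for frequently measured and cardiac endpoints alike

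*SAP*

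**What the plan says.** SAP Appendix 2 holds two blocks of sample code. The single-arm block, written for percent predicted FVC, has "model chgfvc = avisityr fvc0/solution cl covb outp=pred_fvc cl" and "random intercept avisityr /subject=subjid type=CS". The block for the comparison with natural history data has "MODEL chg = trt|avisityr base/ SOLUTION DDFM=KR". The first leaves the degrees of freedom (df) to the software; the second asks for Kenward-Roger (KR).

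SAP 9.2.2 carries the single-arm model to six endpoints: "The following endpoints will be analyzed with the same RCM analysis method". They are FVC, PUL, grip strength, cardiac fibrosis score, LVEF and circumferential strain. SAP 9.2.2.1 lists the output: "The LSMean (SE) and 95% CI for annual change (slope) as well as estimated changes from baseline at year-1", and the same for years 2 to 4. SAP 5.1 adds that "all confidence intervals will be two-sided 95% confidence intervals". Neither 9.2.2.1 nor 9.2.4 names a df method, so the sample code is the only specification.

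The year-by-year changes come from lines such as "ESTIMATE 'Change from Baseline at Year 4' intercept 1 avisityr 4 fvc0", in which the baseline covariate is the last effect named.

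The trial is small. The Protocol synopsis says: "Approximately 22 subjects will be enrolled; interim analysis may increase sample size to approximately 32". The number entering the OLE is not given.

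**The concern.** With about 20 subjects, the choice of df visibly changes the t multiplier. The sponsor applies a small-sample correction in the external comparison but not in the model that gives the trial's own slopes and year 1–4 changes, and gives no reason. Following the code as written would put corrected intervals in one table and uncorrected intervals in another, although both come from essentially the same model and subjects. The uncorrected year 1–4 intervals would look more precise than the number of subjects supports.

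**Working it through.** **Nothing to reproduce.** The documents state no df and no interval width. The check compares what the code as written would give with what KR would give.

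**Inputs from the documents**
- Random intercept and slope by subject, with baseline as a fixed effect (SAP 9.2.2.1, Appendix 2).
- Cardiac MRI yearly in the OLE: up to 4 post-baseline values (SAP Appendix 1, Table 3). With the main-study scans at Weeks 52, 104, 156 and 208 (Protocol Appendices 2–4), up to 8.
- Pulmonary function: up to 16 post-baseline values in the main study (Protocol Appendices 1–4) plus 8 in the OLE, so up to 24.
- Time span: SAP 9.2 runs from the main-study baseline to the last OLE visit, but 9.2.2.1 speaks of years 1 to 4 in the OLE period. Both readings are covered below.

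**Assumptions**
- n = 20 OLE subjects, with other values of n shown for range.
- The PROC MIXED default is containment, and an ESTIMATE line takes the df of its last listed effect.

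**Default df.** Let n be the number of subjects and m the post-baseline values per subject.
- Slope: the random slope contains avisityr, so df = n − 1 = 19.
- ESTIMATE lines: fvc0 comes last and no random effect contains it, so df = N − rank[X Z] = nm − 2n.

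**Comparator.** KR df is about n − 1 to n − 2, so 19 to 18, with t = 2.093 to 2.101.

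**Year 1–4 changes, complete data, n = 20.** KR widening = t(KR df) / t(default df) − 1, with equal standard errors.

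| m | Default df | t | KR interval wider by |
|---|---|---|---|
| 3 | 60 − 40 = 20 | 2.086 | 0.3–0.7% |
| 4 | 80 − 40 = 40 | 2.021 | 2.093/2.021 to 2.101/2.021: 3.6–4.0% |
| 8 | 160 − 40 = 120 | 1.980 | 2.093/1.980 to 2.101/1.980: 5.7–6.1% |
| 24 | 480 − 40 = 440 | 1.965 | 2.093/1.965 to 2.101/1.965: 6.5–6.9% |

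The gap grows with the number of measurements, because residual df rises while the number of subjects does not.

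**Other n**
- n = 15, m = 4: default df 30, t = 2.042. KR t = 2.145 to 2.160, so 5.0–5.8% wider.
- n = 22, m = 4: the default is 3.1–3.4% narrower, so KR is 3.2–3.5% wider.
- n = 32, m = 8: default df 256 − 64 = 192, t = 1.972. KR t = 2.040 to 2.042 (31 to 30 df), so about 3.4–3.6% wider.

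**Simulation** (n = 20, REML, KR standard errors and df computed directly; variances and dropout are assumed)
- Year-4 change, 8 scans, everyone kept at least two years: default df about 64–100 against KR 17–19; KR 5.5–6.7% wider.
- Year-4 change, FVC, main study plus OLE: default df about 380 against 19; KR 6.5–6.8% wider.
- Year-4 change, 4 scans: about 3% wider under compound symmetry, rising to about 7% with unstructured covariance, dropout and noisier measurements.
- Slope, FVC: about 0–1% wider.
- Slope, yearly MRI, 12% a year dropping out after OLE entry: 0.2–4.2% wider with unstructured covariance, and −0.9% to 3.0% with compound symmetry. At 20% a year, 2–6%.

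**The case against.** The strongest reply is that little hangs on this. The code is labelled as a sample, Protocol Appendix 6 calls for descriptive summaries of the extension data, and no OLE success criterion turns on these intervals. That stands, and it keeps the point minor. It does not remove the inconsistency, because the sample code is the only place where a df method appears.

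A second reply is that the sizes rest on software defaults, an assumed number of subjects and assumed variances. That also stands, so ranges are given rather than one figure. Coverage evidence is weak too: in simulation the default covered 92–96% and KR 94–98%, and with 250 data sets the Monte Carlo standard error near 95% is √(0.95 × 0.05/250) = 1.4 points. The case rests on the df mismatch, not on coverage.

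A reader might infer that the cardiac intervals in particular are about 7% too narrow because scans are sparse, with FVC largely spared. The documents do not support that. For slopes, such a gap needs dropout from time zero over a long series of scans. OLE entry requires completed treatment through the primary endpoint (SAP 2), and subjects who withdraw before Week 104 are ineligible (Protocol 7.1.4). For the year 1–4 changes on complete data the contrast runs the other way: more measurements give a larger gap.

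A reader might also link this to the Protocol's success rule at Week 104. That analysis belongs to the main-study SAP, of which only the addendum is in the documents. Nothing here shows that it is affected.

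**Conclusion.** The inconsistency is real and its consequence is modest. As coded, the year 1–4 intervals would use far more df than about 20 subjects can supply. KR intervals would be roughly 5–7% wider when main-study data are included, and about 3–7% wider with only four MRIs. FVC is affected as well as the cardiac endpoints. PUL and grip strength should be too, since they are measured often. Slope intervals, which carry the annual-change endpoints themselves, move by about 0–1% for FVC and about 0–4% for yearly MRI, up to about 6% with higher dropout.

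These sizes rest on the PROC MIXED defaults described above, about 20 OLE subjects, and assumed variances and dropout. A larger OLE would shrink them. The same block also uses compound symmetry where 9.2.2.1 calls for an unstructured matrix first. That is a separate conflict; under compound symmetry the gaps tend to be somewhat smaller.

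**What to change.** Add DDFM=KR to the MODEL statement of the first block in SAP Appendix 2. In 9.2.2.1, state that Kenward-Roger standard errors and df are used for all model-based RCM analyses, for both slopes and year 1–4 changes. Write in an exception for the sandwich-estimator fallback that 9.2.2.1 allows, because KR corrects the model-based standard error and does not go with it; name the df to be used in that case.

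The cost is one code option and a sentence or two. No extra data are needed, and the reported intervals become slightly wider.

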9.2.4. Exploratory Analysis - Comparison with the CINRG natural history data

Efficacy endpoints: % predicted FCV (ppFVC), LVEF, and grip strength in dominant hand will be compared with a subset of CINRG DMD Natural History study (DNHS) data with all 36 subjects using a random coefficient model (RCM). The other outcome measures including Performance of Upper Limb (PUL), cardiac fibrosis by LGE, and Myocardial Circumferential Strain [Mean Peak Circumferential strain (MPCS) and Global Circumferential Strain (GCS) percentage] assessed by cardiac MRI are not available in CINRG data and therefore will not be compared.. The RCM model will use efficacy data from both the main and OLE periods and include continuous variable avisityr (calculated as the elapsed days of assessment date from main study baseline date in the unit of year), treatment trt (079 subjects as treated with trt = 1, and subjects in CINRG data as control with trt =0), the interaction term of trt and avisityr, and baseline endpoint as fixed effects, while the intercept and avisityr are included as random effects. The strategy for covariance structure for the within-patient errors in the model is the same as what is described in [Section 9.2.2.1](#). The LSMean (SE) for annual change (slope) as well as LSMean (SE) and 95% CI of treatment differences between pamrevlumab and control of estimated changes from baseline at year 1, year 2, year 3 and year 4 in the OLE period will be presented. The sample SAS code is provided in [Appendix 2](#).

Line plots of each subject's efficacy trajectory compared with the mean plot of the CINRG will be provided.

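### The sample code for the single-arm random coefficient model uses compound symmetry for the random intercept and slope, while the SAP text starts from an unstructured covariance

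*SAP*

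**What the plan says.** SAP Section 9.2.2.1 gives the rule for the single-arm RCM: "The unstructured covariance structure for the within-patient errors in the model will be applied first". If that does not converge, five structures follow in order: "heterogeneous Toeplitz, homogeneous Toeplitz, first-order autoregressive, compound symmetry, and variance component". CS is therefore the fourth fallback. The required output is "The LSMean (SE) and 95% CI for annual change (slope) as well as estimated changes from baseline" at years 1 to 4. Section 9.2.2 applies the method to six listed endpoints.

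Appendix 2 introduces its first block with "SAS code for this model, using the primary endpoint ppFVC as example, is provided below" and writes "random intercept avisityr /subject=subjid type=CS". No comment or macro variable marks this as a fallback. The second block, for the natural history comparison, writes "RANDOM intercept avisityr / SUBJECT =SUBJID TYPE=UN GROUP= trt". Section 9.2.4 puts that model under the same rule: "The strategy for covariance structure for the within-patient errors in the model is the same as what is described in" Section 9.2.2.1.

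**The concern.** Two code blocks governed by one rule start from different covariance structures, and only the second agrees with the rule. The SAP does not say whether text or code prevails. A programmer who follows the text and one who runs the block as printed would report different standard errors and intervals from the same data.

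The printed choice is also hard to defend as a model. With CS, the variance of the intercept (percentage points squared) must equal the variance of the slope (percentage points per year, squared). Nothing in the disease or the design suggests that these should be equal. What is at stake is the reported precision of the long-term slope and of the year 1 to 4 changes.

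**Working it through.** **1. Which matrix the code constrains.** Section 9.2.2.1 speaks of within-patient errors. Neither block has a `REPEATED` statement, so `TYPE=` on the `RANDOM` line acts on the matrix G of random intercept and slope, with V = Z G Zᵀ + σ²I for each subject. On either reading of the text, the first block does not apply unstructured first.

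**2. What CS imposes.**
- Unstructured has three parameters: intercept variance, slope variance, covariance.
- CS has two: one common variance, one covariance.
- On a two-by-two matrix, heterogeneous Toeplitz is the same model as unstructured. Homogeneous Toeplitz, AR(1) and CS are one model apart from parameter bounds.

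**3. The constraint depends on the time unit.** Take an intercept SD of 2.12 and a slope SD of 3.39 per year (row B below), a ratio of 2.12/3.39 = 0.63. In weeks, the slope SD is 3.39/52.18 = 0.065 and the ratio is 2.12/0.065, about 33. Unstructured fits equivalently in either unit. CS is a different model in each.

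**4. Why the standard error can move either way.** For a complete subject the slope has variance of about σ₁² + σ²/Sxx, where σ₁ is the slope SD and Sxx the spread of visit times. CS replaces σ₁² by a compromise between intercept and slope variance. The slope SE is then too small if the intercept SD is below the slope SD, and too large if it is above.

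**5. Illustration.** The documents give no variance components for this model. Protocol Section 9.1 gives only a total SD of 5 for change in percent predicted FVC, as a planning value for the main-study t-test. All components below are assumed.

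Rows A to D cover main study plus OLE:
- n = 22 and 250 REML replicates
- true slope −3 per year, OLE from week 104, 10% yearly dropout in the OLE
- slope variance + 1.5 × error variance = 25; for A, 4.36² + 1.5 × 2² = 19 + 6 = 25
- the intercept spread is baseline error only, from two sessions: error SD/√2

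| Case | Slope SD | Error SD | Intercept SD | Intercept/slope | CS/UN slope SE | CS/UN year-4 SE |
|---|---|---|---|---|---|---|
| A | 4.36 | 2 | 1.41 | 0.32 | 0.78 | 0.79 |
| B | 3.39 | 3 | 2.12 | 0.63 | 0.88 | 0.89 |
| C | 2.57 | 3.5 | 2.47 | 0.96 | 0.99 | 0.99 |
| D | 1.0 | 4 | 2.83 | 2.83 | 1.32 | 1.25 |
| B + true intercept SD 3 | 3.39 | 3 | √(4.5+9) = 3.67 | 1.08 | 0.99 | – |
| B + true intercept SD 5 | 3.39 | 3 | √(4.5+25) = 5.43 | 1.60 | 1.31 | – |
| B + true intercept SD 8 | 3.39 | 3 | √(4.5+64) = 8.28 | 2.44 | 1.74 | – |

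The last three rows do not hold the total SD at 5. A separate set of 40 replicates gave 1.04, 1.26 and 1.83 for them.

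A different set-up (n = 15, eight visits 24 weeks apart, no dropout, 200 replicates) gave these slope-SE ratios:
- 0.89 for intercept and slope SDs of 1 and 4
- 1.00 for 2 and 2
- 1.51 for 6 and 2
- 1.81 for 6 and 1
- 2.46 for 8 and 2

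With OLE visits only and the total SD held at 5, the ratios were 0.85, 1.03 and 1.19 for slope and error SDs of (4.12, 2), (2.65, 3) and (1.37, 3.4). On a yearly MRI schedule they were 0.87, 1.00, 1.06 and 1.09 when the intercept SD was 0.5, 1, 2 and 3 times the slope SD.

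**6. Other outputs, cases A to D.** The year-1 SE ratios were 1.03, 1.04, 1.01 and 0.82. In D, one fit thus gives a slope interval that is too wide and a year-1 interval that is too narrow. CS slope coverage was 88, 88, 95 and 98%, with Monte Carlo error of about 1.4 to 2.1 points. The mean absolute shift in the slope estimate was only 0.01 to 0.04 points per year.

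**The case against.** **It is sample code.** Appendix 2 is headed as such, the rule in Section 9.2.2.1 is explicit, and CS lies within the permitted sequence. This stands in part: the block does not prove what was run. But it is presented as the code for this model, with no fallback note. The SAP Addendum (Sections 1 and 2) also records that SAP version 1.0 specified two-sided p-values while the function in its appendix returned one-sided ones, and that the related tables and figures had to be amended. Appendix code has therefore already affected reported output in this study.

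**CS is where the rule leads anyway.** On the two-by-two matrix, CS is the first model in the sequence that truly differs from unstructured. That is correct, but it applies only after non-convergence. In the main-plus-OLE simulations at n = 22, the unstructured matrix was near-singular in 0 to 2% of trials. It was so more often with OLE visits only (3 to 16%) and MRI (6 to 22%), so a real fallback is plausible there.

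**The window is unsettled.** Section 9.2 runs by default from main-study baseline to the last extension visit. Section 9.2.2.1 refers to years 1 to 4 in the OLE period, the code comment counts from Day 1, and Section 13 sets Day 1 at the first OLE dose. This stands. The OLE-only ratios are milder.

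**A reader might infer that the printed code systematically understates uncertainty, or that cases A and D bound the error.** The documents support neither. Those cases assume no true intercept variance, and adding some takes the ratio in case B from 0.88 to above 1.7.

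**Conclusion.** The text and the code contradict each other, and the first block is wrong as printed. It imposes an unjustified, unit-dependent equality of variances on the results that Section 9.2.2.1 requires. The effect is on standard errors and intervals, in either direction. Illustrative slope-SE ratios run from about 0.8 to above 1.7 (2.46 in the most extreme case tried), and are close to 1 when the intercept and slope SDs are similar. These figures rest wholly on assumed variance components, sample size and visit pattern, and are not bounds.

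The consequence is limited. Point estimates barely move, and Protocol Appendix 6, Section 5 treats extension data descriptively. A reader might also infer that the Week 104 primary conclusion is in doubt. It is not: this SAP covers the OLE, and the success rule in Protocol Sections 9.1 and 9.4.1 does not depend on this block.

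**What to change.** 1. Change `TYPE=CS` to `TYPE=UN` in the first block of Appendix 2.
2. State in Section 9.2.2.1 that the covariance sequence applies to the random-effects matrix, and that CS is used only after unstructured fails to converge.
3. Report the structure used with each RCM result.

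The cost is one keyword, two or three sentences and a table footnote. No data, visit or sample size changes. Intervals widen where CS would have been too narrow and narrow where it would have been too wide.
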